2.2.1 Rationale and design

The antiseptic povidone-iodine can safely be instilled into the pleural for the purpose of pleurodesis^[6]. Pleural irrigation with antiseptics is used in adults with open drainage for chronic empyema^[7] and has been described in the acute management of paediatric pleural infection^[8].

This sub-study will investigate the safety and usefulness of povidone-iodine pleural irrigation in 15 eligible patients recruited to PICS. A matched control group will be used and will be composed of 15 patients previously recruited to PICS without receiving povidone-iodine pleural irrigation.

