2.1.3 Eligibility

All adult patients admitted with pleural infection who are willing to sign an informed consent will be recruited. Pleural infection will be defined by the presence of one of the following: a)

the presence of pus in the pleural space; b) positive pleural fluid gram stain or culture; or c) pleural fluid pH < 7.2 or pleural fluid glucose < 40 mg/dL in the setting of acute respiratory infection.

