2.1.5 Study assessments

PICS is a strictly observational study and all data gathered will be related to the patient's clinical care. The following data will be collected:

- Average age and gender proportion of patients admitted (from screening log)
- Comorbidities
- RAPID score
- Baseline blood tests and follow up inpatient tests (minimum urea and electrolytes, full blood count, C-reactive protein, and serum albumin)
- Pleural fluid results
- Microbiological results (pleural fluid and blood)
- Ultrasound findings
- CT findings if available
- Baseline and follow up CXRs
- Treatments received for pleural infection
- Length of hospital stay (LOS)
- Outcome at discharge (medical, surgical, dead)

Medical treatment will include: thoracentesis, chest drain, fibrinolytic, medical thoracoscopy

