2.2.2 Additional eligibility criteria

- Inclusion criteria:

- Unilocular pleural collection

- Exclusion criteria:

- Known or suspected thyroid disease
- Allergy to iodine
- Persistent large collection on follow up imaging 24-48 of post tube insertion that is deemed to require another drainage procedure

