2.2.3 Specific assessments

- Two applications of 100-250 ml solution of 2% povidone-iodine will be irrigated into the pleural space of eligible patients 12 hours apart. The tube will be clamped for 15 minutes after irrigation and the patient will be asked to change position frequently during this period. The first dose will be applied 24-72 hours after tube insertion.

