2.2.4 Outcomes

- Safety: incidence of adverse events (new chest pain, fever, dyspnoea or desaturation) within 24 hours from the first irrigation

- Efficacy

- Time to defervescence
- Time to chest tube removal
- Length of hospital stay
- Need for additional aspiration/tubes

_ Failure of medical treatment

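### Controls are not required to meet the sub-study criteria or to be still drained at the 24-72 h point that irrigated patients must reach, and the efficacy times have no common start, so the efficacy comparison is open to selection and immortal-time bias

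*Protocol*

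**What the plan says.** **Control group (Protocol 2.2.1).** "A matched control group will be used and will be composed of 15 patients previously recruited to PICS without receiving povidone-iodine pleural irrigation". Section 2.2.1 applies the word 'eligible' to the 15 irrigated patients, not to the controls.

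**Source of controls.** Cohort entry (2.1.3) is broad: "All adult patients admitted with pleural infection who are willing to sign an informed consent will be recruited". No chest tube is needed to enter, and a drain is one of several treatments in 2.1.5: "Medical treatment will include: thoracentesis, chest drain, fibrinolytic, medical thoracoscopy".

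**What an irrigated patient must pass after tube insertion.**
- Section 2.2.2 excludes a patient with: "Persistent large collection on follow up imaging 24-48 of post tube insertion that is deemed to require another drainage procedure". (The unit after 24-48 is not printed; hours is the natural reading.)
- Section 2.2.3: "The first dose will be applied 24-72 hours after tube insertion". This can bind irrigated patients only, because controls receive no dose.

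**Outcomes (2.2.4).** Safety has a start: "within 24 hours from the first irrigation". The efficacy list, which includes "Time to chest tube removal" and "Need for additional aspiration/tubes", has none.

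**Analysis (4.0).** Plain two-group tests: t or Mann-Whitney for continuous variables, chi-squared or Fisher for categorical ones.

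**The concern.** The irrigated group is defined partly by what happened after drainage began. Its members did not need early re-drainage, and their tube stayed in until the first dose. If controls do not pass through the same two filters, the groups can differ when irrigation does nothing.

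- **Re-drainage.** Early need for another procedure removes a patient from the irrigated group. In a control it could count as an efficacy event. This would favour irrigation.
- **Tube time.** On a clock from insertion, an irrigated patient cannot have had the tube removed before the first dose, whereas a control can. That interval is immortal time, and it makes irrigated tube times look longer.

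At stake are the efficacy estimates of a non-randomised comparison of 15 with 15. Naming matching variables can be left to an SAP. Who may serve as a control is a design rule, and 2.2.1 sets it incompletely.

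**Working it through.** The protocol gives no event rate, tube-time distribution, significance level or effect size, so it has no figure of its own to reproduce. From the protocol: 15 per group and a first dose at 1-3 days. Everything else is assumed: no true effect, two-sided 0.05, and the values below.

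**1. Additional procedures, if 2.2.2 does not bind controls.** Let q be the risk of early re-drainage and r the later risk. Irrigated risk = r. Control risk = q + (1 - q)r. With r = 0.10, exact Fisher enumeration gives:

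| q | Control risk | Irrigated risk | Rejection |
|---|---|---|---|
| 0 (also the result if 2.2.2 binds controls) | 0.10 | 0.10 | 0.6% |
| 0.10 | 0.10 + 0.90 × 0.10 = 0.19 | 0.10 | 3.4% |
| 0.20 | 0.20 + 0.80 × 0.10 = 0.28 | 0.10 | 12.2% |
| 0.30 | 0.30 + 0.70 × 0.10 = 0.37 | 0.10 | 26.7% |

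Rejection reaches 5% at q of about 0.125. With r = 0.05 it does so at about 0.13, and with r = 0.20 at about 0.15.

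**2. Tube time, selection on the first dose only.** Tube time T is lognormal with SD of log T 0.6, and the first dose D is uniform on 1-3 days. A patient can be irrigated only if T > D. The clock runs from insertion in both groups, and the test is Mann-Whitney over 20,000 simulated trials.

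| Median T | Tube out before D | Mean, controls | Mean, irrigated | Shift | Rejection |
|---|---|---|---|---|---|
| 4 d | 13.7% | 4.79 | 5.27 | +0.48 d | about 8% |
| 5 d | 7.6% | 5.99 | 6.33 | +0.34 d | about 6% |
| 7 d | 2.6% | 8.38 | 8.55 | +0.17 d | about 5% |

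The control mean follows from median × exp(0.6²/2); for example, 4 × 1.197 = 4.79.

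**3. The same, if 2.2.2 binds controls and is taken to mean a tube in place at imaging** (imaging assumed uniform on 1-2 days). The shifts fall to about 0.27, 0.22 and 0.13 days, with rejection of about 5-6%.

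**4. Both selections together.** Early re-drainage of 10, 20 and 30% is assumed to lengthen tube time 1.5-fold; such patients occur among controls only.

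| Median T | q = 10% | q = 20% | q = 30% |
|---|---|---|---|
| 4 d | +0.24 d | 0.00 d | -0.24 d |
| 5 d | +0.04 d | -0.26 d | -0.55 d |
| 7 d | -0.25 d | -0.67 d | -1.09 d |

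Rejection stays at about 4-6.5%. The sign therefore depends on inputs that the protocol does not supply.

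**5. With the remedy.** Controls are required to be still drained at an assigned first-dose time, and both groups are counted from it. Mean remaining tube times then agree within 0.03 days, and rejection is about 4-5%.

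**The case against.** **The word 'matched' and the heading of 2.2.2 may already cover this.** Matching could include tube status, and 2.2.2 is headed as eligibility for the sub-study, of which controls are part. This is a fair reading, and under it the re-drainage bias essentially vanishes. It is not stated, however, and 2.2.2 still does not require the tube to be in place at the first-dose time. A smaller tube-time shift remains (step 3).

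**Controls must have had a tube anyway.** A reader might infer from 2.1.3 and 2.1.5 that controls could be patients who never had one. Listing tube removal as an efficacy outcome already implies drained controls, so that inference is weak. The open question is whether they were still drained at a comparable time.

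**Start times belong in an SAP.** This stands: a missing start alone would be no finding. It matters here because the one start given, first irrigation, does not exist for controls. A reader might go further and suppose that irrigated times run from first dose and control times from insertion. Simulated rejection would then be about 19-59% over a range of assumed inputs, with irrigated times appearing shorter. No section states different starts for the two groups, so those rates cannot be attributed to the plan.

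**The effect is small beside the noise.** This largely stands for tube time. With the step 2 inputs, the standard error of a 15 v 15 mean difference is about 1.2, 1.4 and 2.0 days, so the shifts there are at most 0.48/1.15, or about 0.4 of a standard error. The largest shift in step 4 is about half of one (1.09/2.0).

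**Conclusion.** The gap is real but limited. As written, 2.2.1 does not hold controls to the post-insertion conditions that irrigated patients must meet, 2.2.4 sets no common start, and the tests in 4.0 do not correct for either.

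- The larger bias, in additional procedures, arises only if 2.2.2 does not bind controls. Even then it exceeds nominal rejection only when early re-drainage is above roughly 13-15%.
- On a common clock from insertion, the tube-time shift is about 0.1-0.5 days against irrigation, and selection on early re-drainage can cancel or reverse it. The main harm is a shifted estimate, since false-positive rates stay near nominal in most scenarios.
- The protocol does not support a claim that the design is bound to produce a false result in favour of irrigation.
- The 24-hour safety outcome is not affected.

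Every size rests on assumed rates and distributions. Severity: minor to moderate.

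**What to change.** **Add to 2.2.1:** *Each control must meet the 2.2.2 criteria as at its own post-tube imaging and, at a time since tube insertion equal to the first-dose time of its matched irrigated patient (or a time assigned from the irrigated patients' first-dose times), still be drained, unoperated and without a further drainage procedure.*

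**Add to 2.2.4:** *Time to chest tube removal, additional aspiration/tubes and failure of medical treatment are counted from that time point in both groups; the other efficacy times use one stated start common to both groups.*

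**Record** tube insertion and removal dates and dates of further procedures for drained PICS patients. The list in 2.1.5 does not expressly name them.

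**Cost.** A few sentences and form fields. For controls already enrolled, some dates must be retrieved from hospital records, because section 3.0 keeps no source data in the trial files. The control pool also shrinks. If 10-30% fail the imaging criterion and 3-14% have lost the tube by the assigned time (assumed, independent), the drained unilocular candidates needed for 15 controls run from 15/(0.90 × 0.974) = 17.1 to 15/(0.70 × 0.863) = 24.8. That is about 17-25, before further losses to matching. No dose or clinical rule changes.

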2.1.4 Consenting and co-enrollment

In the TwiC design patients are consented to take part in the cohort study with the possibility of being randomized in the future into trials without being specifically told if a given eligible participant is randomized into a control arm of a trial^[5].

The consenting process for PICS will involve obtaining consent for the core observational part of the study. There will be a separate clause asking for permission to enroll a participant into an interventional trial if the participant meets the eligibility criteria. Participants will have the opportunity to accept taking part in PICS and reject taking part in interventional trials. The consent form will be modified to include clauses for any new trial anchored to the PICS platform. Participants will be given clear written information about PICS and any additional trials and will be given enough time consider taking part.

All consenting eligible participants for an interventional trial will be informed in case they are randomized to a given trial regardless of the arm they are randomized to. In all cases, a single participant will not be enrolled into more than one interventional trial at the same time.

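### Section 2.2.1 lets PICS patients who declined interventional trials serve as controls, although every irrigated patient must have accepted them, so the two groups can differ by willingness to enter a trial.

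*Protocol*

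**What the plan says.** Protocol section 2.1.4 separates consent to the cohort from consent to trials: "There will be a separate clause asking for permission to enroll a participant into an interventional trial if the participant meets the eligibility criteria". It then says what a refusal means: "Participants will have the opportunity to accept taking part in PICS and reject taking part in interventional trials". A refuser therefore remains a full member of the cohort. The form can also change over time: "The consent form will be modified to include clauses for any new trial anchored to the PICS platform".

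Section 2.2.1 sets up the sub-study as "povidone-iodine pleural irrigation in 15 eligible patients recruited to PICS" and defines the comparison group as follows: "A matched control group will be used and will be composed of 15 patients previously recruited to PICS without receiving povidone-iodine pleural irrigation". Matching apart, a control has to meet two conditions: earlier recruitment to PICS and no irrigation. The answer to the trial clause is not one of them, and the matching variables are not named.

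Section 2.2.2 adds clinical criteria only. Section 4.0 compares the study arms with a t-test or Mann-Whitney test for continuous variables and a chi-squared or Fisher test for categorical ones, with no adjustment.

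**The concern.** The irrigated group passes through a filter that the control group need not pass. Patients who agree to an experimental procedure and patients who decline it may differ in ways that bear on the efficacy outcomes in section 2.2.4, such as length of stay, time to tube removal and failure of medical treatment. The protocol offers no evidence on whether they do. If they do, the difference lies along the treatment contrast, because refusers can appear on one side only.

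At stake is one avoidable source of imbalance in a comparison of 15 with 15 that has no randomisation to protect it. Who may be a control is a design rule. The protocol has fixed that rule, and fixed it more broadly than it needs to, so this is not a detail left to an analysis plan.

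**Working it through.** The protocol gives no calculation behind 15 versus 15 and no refusal rate, so there is no figure to reproduce. The check is a reading of the sections together, followed by an illustration.

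**Who can be in each group**

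| Condition | Irrigated (15) | Controls (15) |
|---|---|---|
| Consented to the PICS core | yes | yes |
| Accepted the interventional-trial clause | required (2.1.4) | not required (2.2.1) |
| Irrigated | yes | no |
| Unilocular collection and 2.2.2 exclusions | yes | not stated |
| Recruitment period | not restricted | earlier |

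The second row is the asymmetry. It rests on treating the irrigation sub-study as an interventional trial in the sense of section 2.1.4, which is the natural reading since irrigation is given for the study.

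**How many refusers could be among the controls**

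Let r be the share of refusers in the control pool. It is an assumption, taken as 10% to 40%. Assume also that selection of controls is unrelated to refusal. The expected number is 15 x r, and the chance of at least one is 1 - (1 - r)^15.

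- r = 10%: 15 x 0.10 = 1.5; chance 1 - 0.9^15 = 79%
- r = 20%: 15 x 0.20 = 3; chance 1 - 0.8^15 = 96%
- r = 30%: 15 x 0.30 = 4.5; chance 1 - 0.7^15 = 99.5%
- r = 40%: 15 x 0.40 = 6; chance 1 - 0.6^15 = more than 99.9%

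The irrigated group has 0 of 15 throughout.

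**What that could do to the contrast**

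Let d be the mean outcome of refusers minus that of accepters under the same care. The control mean then shifts by r x d.

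- d = 0: no shift, whatever r is.
- d = 3 days of stay (assumed): 0.10 x 3 = 0.3 days to 0.40 x 3 = 1.2 days.
- d = 10 points in failure rate (assumed): 1 to 4 points.
- d = 30 points in failure rate (assumed): 3 to 12 points.

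The sign of d is unknown. If refusers do worse, irrigation looks better than it is; if they do better, it looks worse.

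**Against the precision available**

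With 15 per group, and assuming a two-sided 5% level and 80% power, the detectable standardised difference is about (1.960 + 0.842) x sqrt(2/15) = 1.02 SD. The protocol gives no SD for length of stay, so the day figures cannot be placed on this scale.

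**The case against.** The strongest reply is that nothing is breached. A control receives no intervention and is not randomised. The treatments, length of stay and discharge outcome of controls are collected under the observational consent (section 2.1.5), and relating treatments to in-hospital outcomes is an aim of PICS itself (section 1.0). The promise to inform reads "All consenting eligible participants for an interventional trial will be informed in case they are randomized to a given trial regardless of the arm", so it does not reach these controls. This stands. A reader might infer that using a refuser as a control contradicts section 2.1.4, or that such controls might have to be withdrawn afterwards. The documents support neither: no sentence bars the use of a refuser's cohort data as a comparator, and no withdrawal rule points that way.

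The second reply is that the bias is unproven. Refusers may be chosen but need not be, the refusal rate and outcome difference are not given, and matching could remove some of the difference. This also stands as to size and direction. It does not remove the asymmetry, because matching on unnamed variables cannot be assumed to cover willingness to enter a trial.

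The third reply is that this is not the main weakness of the control group. Earlier recruitment, the unnamed matching variables and the doubt whether the 2.2.2 criteria apply to controls matter at least as much. That is fair, and the change proposed here leaves them in place. It does remove one difference that is easy to remove.

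**Conclusion.** The point holds as a cheap improvement. Section 2.2.1 admits as controls patients who declined trials, section 2.1.4 means that every irrigated patient accepted them, and neither the stated matching nor the planned tests deals with the difference.

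It would go too far to say that the plan builds a volunteer bias into the result. The documents show that such a difference is possible. They do not show that refusers will be chosen, or that their outcomes differ. The count of 1.5 to 6 refusers rests on an assumed 10-40% refusal and on selection unrelated to refusal; the shifts in days or percentage points rest on a further assumed outcome difference. These figures illustrate the mechanism and are not estimates for this study.

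**What to change.** Amend section 2.2.1 along these lines: *The 15 controls are matched PICS patients from earlier recruitment who gave the general interventional-trial permission on the consent form and were not irrigated. The comparison with the irrigated group is non-randomised.* Report how many otherwise suitable controls were set aside because they had refused.

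The wording should point to the general clause, not to an irrigation-specific one. Clauses are added as trials join the platform, so earlier recruits may have signed before an irrigation clause existed. The general clause provides the answer needed, and section 3.0 already requires reasons for non-enrolment to be recorded.

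The cost is one phrase and a smaller pool. To keep 15 accepters, the number of otherwise suitable candidates needed is 15/(1 - r): about 17 if 10% refuse and 25 if 40% refuse, before any further loss from matching. In a one-year study at a single centre this leaves less room to match on clinical factors. The remaining selection differences (earlier recruitment, unnamed matching variables, application of the 2.2.2 criteria to controls) are not cured by this change.

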1.0 Background

Pleural infection is a condition that requires hospitalization for management and is associated with significant in-hospital morbidity and mortality^[1]. Predictors of poor outcome include advancing age, poor nutrition, hospital-acquired infection and impaired renal function.^[2] Medical management is centred on appropriate antibiotic treatment and fluid drainage usually by the means of an intercostal tube. Up to 30% of patients fail medical treatment and referred for surgery.^[3] A recent systematic review of adults patient with pleural infection has shown that the demographics of patients with pleural infection are different in patients from high-income vs lower income countries; the latter being of younger age and lower comorbidity burden.^[4] However, the results of the review did not show significant differences in patient outcomes. The same systematic review pointed to the need for more data from patients residing in lower income countries given that the majority of data is contributed by studies from higher income countries.^[4]

This study aims to prospectively investigate the incidence of pleural infection in a large tertiary centre gathering demographic and clinical data about patients recruited. In addition, the study will examine the different treatment offered and how this related to in-hospital outcomes (length of hospital stay, rate of referral to surgery and mortality).

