2.1.2 Design

The study will be designed as a modified trial within cohort (TwIC) study.^[5] PICS will primarily aim to recruit patients prospectively to gather clinical and demographic data on patients admitted with pleural infection in addition to clinical data on tests performed and treatments received as part of the standard care. The in-patient outcomes will be recorded at the time of discharge data or death, whichever is earlier. Within the TWIC design, PICS will be a platform for recruiting patients to interventional trials for eligible patients within the cohort (see 'consenting' section)

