4.0 Statistics

Continuous variables will be compared between the study arms using t-test or Mann Whitney test according to the normality of the study data. Categorical variables (including primary outcome measure) will be compared using the Chi squared test or Fisher exact test as appropriate.

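### Controls are drawn from earlier PICS patients whose stay and discharge outcome may already be on file, and the protocol does not make their selection independent of those outcomes

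*Protocol*

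**What the plan says.** Protocol section 2.2.1 plans to study the safety and "usefulness of povidone-iodine pleural irrigation in 15 eligible patients recruited to PICS". On the comparator it says: "A matched control group will be used and will be composed of 15 patients previously recruited to PICS without receiving povidone-iodine pleural irrigation". The comparison is therefore 15 against 15, not randomised, with controls who entered the cohort earlier.

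Section 2.1.2 fixes when cohort outcomes are captured: "The in-patient outcomes will be recorded at the time of discharge data or death, whichever is earlier". The data list in 2.1.5 includes "Length of hospital stay (LOS") and "Outcome at discharge (medical, surgical, dead").

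Section 2.2.4 names five efficacy outcomes: time to defervescence, time to chest tube removal, length of stay, further aspirations or tubes, and failure of medical treatment. Section 4.0 compares the arms with a t-test or Mann-Whitney test for continuous variables; categorical variables "will be compared using the Chi squared test or Fisher exact test as appropriate".

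The protocol gives no matching variables, no rule for choosing between equally good candidates, and no masking of the selection to outcomes. Section 3.0 deals with confidentiality (study numbers on the forms, a password on the log). It does not separate outcome data from baseline data.

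**The concern.** An earlier recruit who has left hospital or died has a recorded length of stay and discharge outcome before being considered as a control. If two or three such patients match an irrigated patient about equally well, somebody has to pick one, and the protocol allows that pick to be made with the results in view. No intent is needed: a mild tendency to regard the sicker course as the better match moves the comparison.

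The error enters before analysis. The tests in 4.0 take the chosen 15 as given and can neither detect nor correct how they were chosen. One control set serves all five efficacy outcomes, so a selection that leans on stay or discharge outcome carries over to any outcome correlated with them.

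**Working it through.** The protocol states no power, error rate or expected event rate, so there is no planned figure to reproduce. The check has two parts.

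**1. Which outcomes are on file when matching is done**

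| Efficacy outcome (2.2.4) | In the PICS data list (2.1.5)? |
|---|---|
| Length of stay | Yes, listed |
| Failure of medical treatment | Yes, through outcome at discharge (medical, surgical, dead) |
| Further aspirations or tubes | Implied only, through treatments received |
| Time to defervescence | Not listed |
| Time to chest tube removal | Not listed |

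Two of five are documented, and only for candidates already discharged or dead.

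**2. How far selection can move the comparison (illustration)**

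Inputs: 15 per group (2.2.1). A 30% failure rate is assumed; the only related figure is in section 1.0, "Up to 30% of patients fail medical treatment and referred for surgery", which is a background ceiling and not a planning value. Pool size M is assumed. Two-sided 0.05 is assumed.

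*Reachable range, ignoring matching.* With F failures among M candidates, 15 controls contain at least max(0, 15 − (M − F)) and at most min(15, F) failures.

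- M = 15: the whole pool is used, so there is no freedom.
- M = 20, F = 6: minimum 15 − 14 = 1 (1/15 = 7%), maximum 6 (6/15 = 40%).
- M = 30, F = 9: minimum 0 (0%), maximum 9 (9/15 = 60%).
- Selection blind to outcome: expected 0.30 × 15 = 4.5 failures (30%) in each case.

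*Would that be significant?* Take 4/15 failures on irrigation. Fisher's test needs at least 11/15 among controls (p = 0.027; 10/15 gives p = 0.066). The extreme choice from 30 candidates, 9/15, gives p = 0.14. From 45 candidates (14 failures reachable) it gives p = 0.0005.

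*Several equal matches per irrigated patient.* Suppose each irrigated patient has k interchangeable candidates, there is no true effect, and the candidate with the worse outcome is always taken. The apparent control failure rate becomes 1 − 0.7^k. The false-positive rate favouring irrigation for failure is the sum, over all pairs with more control than irrigation failures and Fisher p < 0.05, of Binomial(15, 0.3) × Binomial(15, 1 − 0.7^k). For length of stay (assumed normal after transformation, t-test) it was simulated.

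| k | Apparent control failure | False positives, failure | False positives, length of stay |
|---|---|---|---|
| 1 | 30% | about 1% | about 2.5% |
| 2 | 51% | about 11% | about 37% |
| 3 | 66% | about 34% | about 72% |

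*Partial tendency.* In a simulated pool of 60, making failures twice as likely to be picked as non-failures raises the apparent control failure rate from 30% to 43%, and false positives favouring irrigation from about 1% to 5%.

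**The case against.** The strongest reply is that matching variables, tie-breaks and masking are details a protocol may leave to the analysis plan, which is not at hand. That holds for the list of variables. It does not dispose of the point: taking controls from earlier patients is a design decision made in 2.2.1, and a selection made with outcomes known cannot be repaired at the analysis stage.

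Other parts of the reply stand and limit the claim.

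- A reader might infer that one team gives the irrigation, holds the outcomes and picks the controls. The protocol does not say who does the matching, so this should not be asserted.
- A reader might infer that all control outcomes are already known. Only two of five are documented, and an earlier recruit could still be in hospital.
- A reader might conclude that selection can dictate the result. The pool size is not given, and for failure even the extreme choice from 30 candidates falls short of significance against 4/15.
- The 30% may be too high for this sub-study, because 2.2.2 limits it to unilocular collections and excludes persistent large collections judged to need further drainage.
- Matching narrows the ranges by an amount that cannot be judged without the variables.
- The safety outcome, adverse events within 24 hours of the first irrigation, does not depend on the controls.

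**Conclusion.** The point holds in this form: the protocol fixes a comparator chosen from earlier patients, two of the five efficacy outcomes are on file for those who have left hospital or died, and nothing in the protocol makes the choice independent of them. Where more candidates than controls qualify, every efficacy comparison is open to bias through that choice.

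The size is not known. It is nil with exactly 15 qualifying patients and can grow with the number of near-equal matches. The failure ranges of 7% to 40% (20 candidates) and 0% to 60% (30 candidates) are outer limits that rest on an assumed 30% rate, assumed pools and no matching constraint. The false-positive rates for two or three candidates per patient are worst cases on the same assumptions. They show what the design permits, not that biased selection will occur. The change should be made before any control is chosen.

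**What to change.** Add to section 2.2.1 that:

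- controls must meet the 2.2.2 criteria and are chosen without replacement by a pre-specified rule on baseline variables, for example nearest RAPID score, then pleural fluid findings, with a fixed tie-break such as study number order;
- the choice is made from a list that holds only study numbers and baseline fields;
- the matched list is locked and dated before any outcome is linked to it.

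RAPID score and pleural fluid results are already collected under 2.1.5, and study numbers are assigned under 3.0. Admission date is not on the 2.1.5 list, so study number order is the safer tie-break.

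Cost: a few sentences and no additional patients. The team gives up discretion to reject a match on clinical impression. Because 3.0 has data entered on paper forms, the baseline fields must be transcribed separately from the outcomes, which is a modest amount of extra work.
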